### 3.8.4 Subgroup Analyses

Differences in treatment efficacy will be explored in several pre-defined subgroups: baseline SICI (median split), baseline MEP amplitude (median split), and baseline riluzole use (yes vs. no). Subgroup specific estimates will be obtained by including subgroup, subgroup  $\times$  visit, and subgroup  $\times$  treatment  $\times$  post-baseline visit terms to models for primary and key secondary efficacy outcomes based on the mITT sample.

### 3.8.5 Multiplicity Adjustments

The effect of each dose of ezogabine on the primary efficacy outcome in the mITT sample will be tested at two-tailed  $p < 0.027$  following Dunnett's correction for comparing two active treatments to placebo. If this primary analysis identifies a significant benefit from ezogabine treatment, then testing the key secondary efficacy outcome at  $p < 0.027$  maintains an overall type I error rate at 5% under a closed testing sequential analysis. If significance of the key secondary outcome alone is accepted as evidence of a therapeutic benefit from ezogabine when the primary analysis is not significant, then the overall type I error rate will be limited to 10% or less (depending on the correlation between the primary and key secondary outcomes). Results from analysis of non-key secondary efficacy endpoints, exploratory efficacy endpoints, and subgroup analyses will report nominal, comparison-wise p-values, recognizing that the totality of results will be evaluated in judging the potential efficacy of ezogabine.

### 3.8.6 Missing Data

Baseline values for efficacy endpoints will be determined from the last non-missing data collected prior to the first dose of study medication. The planned mixed model yields estimates that are unbiased conditional on the observed scores under a missing at random assumption. In addition, a secondary analysis of the primary endpoint will use placebo-based multiple imputation of missing data. Additional sensitivity analyses may be pursued to impute missing values or otherwise construct models for unobserved outcomes if more than 20% of participants are missing follow-up data for any reason.

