### 8.1 Screening Visit

The following procedures will be performed at an office visit to determine the subject's eligibility for the study:

- Obtain written informed consent
- Assess inclusion and exclusion criteria. If ineligible, record reason for screen failure.
- Collect demographic data
- Obtain medical history
- Obtain ALS diagnosis history
- Assign a Global Unique Identifier (GUID)
- Review and document concomitant medications and therapies
- Assess and document AEs that occur after subject signs ICF
- Perform physical examination
- Perform neurological examination, including MMT
- Measure vital signs including height and weight
- Administer ALSFRS-R questionnaire
- Administer the American Urological Association (AUA) Symptom Score survey
- Perform SVC
- Perform hand held dynamometry (HHD) APB bilaterally
- Complete Edinburgh Handedness Inventory- Short Form
- Perform neurophysiological testing (TMS and NCS)
- Collect blood samples and urinalysis for safety clinical laboratory assessments, pregnancy test (WOCBP)
- Perform 12-lead ECG
- Schedule Ophthalmologic visit (visit must be completed within 14 days prior to baseline visit)

- Schedule the Baseline Visit

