 Study staff should document the time the last dose of ezogabine was administered.

Adverse events that occur AFTER signing the informed consent form will be recorded.

 Vital signs include systolic and diastolic pressure in mm Hg, respiratory rate/minute, heart rate/minute and temperature.

 Height measured at Screening Visit only.

 Labs include Hematology (CBC with differential), Complete Chemistry Panel, Liver Function Tests, Urinalysis and serum pregnancy test (WOCBP, screening visit only).

 Blood for iPSC lines can be collected at either week 4, 6 or 8.

 Ophthalmologic Examinations may be scheduled separately, but within 14 days prior to Baseline Visit and within 14 days of Week 12 Visit.

 Subjects will be called at the designated time points, as a reminder to escalate up or taper off study drug, when appropriate.

 Randomization should occur at or prior to the Baseline Visit.

 Administer first dose of study drug AFTER all Baseline Visit procedures are completed (with the exception of ECG testing). Subjects to take study drug until the Week 10 call.

 Review dosing diary

 Muscle symptoms will be completed every day, starting at the Baseline visit, with a Muscle Symptom Diary and should be reviewed by study staff at every visit after Baseline.

 ECG testing should be performed 3 hours post initial study drug administration.

 Lumbar puncture is optional

 Only participant enrolled prior to protocol version 4 were scheduled to complete TMS and TTNCS testing at the week 4 and 12 visits.

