### 3.8 Efficacy Analysis

#### 3.8.1 Primary Analysis of the Primary Efficacy Endpoint

The primary efficacy analysis will be performed on SICI of the APB after log-transformation in the mITT sample of ALS participants and will use a shared-baseline mixed model with fixed effects for visit (6 levels: Screening, Baseline, and Weeks 4, 6, 8, and 12), treatment group (3 levels: placebo and 600 and 900 mg/day ezogabine) x post-baseline visit (4 levels) and random site-specific intercepts and random participant-specific intercepts and slopes with unstructured covariance. The interaction between fixed effects for treatment group and visit will be restricted to post-baseline visits by including a numeric indicator variable (0 pre-treatment, 1 post-treatment) in the interaction. Use of a shared baseline reflects the true state of the population sampled prior to randomization and has the advantage of adjusting for any chance differences at baseline in a manner similar to analysis of covariance (Liang and Zeger, 2000) with potentially greater efficiency with more than one follow-up visit and drop-out. Random participant-specific slopes will be estimated per month from treatment initiation with all pre-treatment observations assigned a value of 0 months from treatment initiation. Data from Final Safety or Early Termination visits will be assigned to the next scheduled post-baseline visit. The following SAS code specifies the model:

```
proc mixed data=xxx method=reml;
  class site id trrnd visit;
  model Value = visit post*trrnd*visit;
  random intercept / subject=site type=vc;
  random intercept month / subject=id(site) type=un;
```

Treatment-dependent differences in the change from pre-treatment to the average of the week 6 and 8 visits on SICI will be estimated by a linear contrast and tested using a two-tailed Wald-test at alpha = 0.027. The following SAS code specifies the linear contrasts used to obtain the two co-primary estimands (with the sort order for treatment group being placebo, 600 mg/day ezogabine, and 900 mg/day ezogabine, and the sort order for visit being chronological):

```
estimate "2|600vsPlb|dAvg 6&8"
  post*ttrrnd*visit 1 1 0 -1 1 0 -1 -1 0 1 1 0 0 0 0 0 0 / cl divisor=2;
estimate "2|900vsPlb|dAvg 6&8"
  post*ttrrnd*visit 1 1 0 -1 -1 0 0 0 0 0 0 -1 1 0 1 1 0 / cl divisor=2;
```

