### 3.8.2 Secondary Analyses of the Primary Efficacy Endpoint

Several secondary analyses will be investigated to assess sensitivity of our estimates of treatment effect to alternative modeling assumptions.

- Active vs. placebo: A secondary estimand of the efficacy of ezogabine will compare both 600 mg/day and 900 mg/day treatment arms vs. placebo, tested at alpha = 0.05. The following SAS code specifies the linear contrast for this comparison:

```
estimate "2|ActvsPlb|dAvg 6&8"
  post*ttrrnd*visit 2 2 0 -2 -2 0 -1 -1 0 1 1 0 -1 -1 0 1 1 0 / cl divisor=4;
```

- Random-slopes model: The visit-specific fixed effects will be replaced with a continuous predictor of month since treatment initiation. Data from Final Safety and Early Termination visits will be placed at their observed follow-up time. Only assessments completed through Week 10, the end of planned study drug exposure, will be included. The following SAS code specifies the model and the linear contrasts used to estimate treatment-dependent differences in rate of change per month:

```
proc mixed data=xxx method=reml;
  where visit in ("Screening","Baseline","Week 04","Week 06","Week 08","Week 10");
  class site id ttrrnd;
  model Value = month ttrrnd*month;
  random intercept / subject=site type=vc;
  random intercept month / subject=id(site) type=un;
estimate "2|600vsPbl|Slope/mn" intercept 0 month 0 ttrrnd*month -1 1 0 / cl;
estimate "2|900vsPbl|Slope/mn" intercept 0 month 0 ttrrnd*month -1 0 1 / cl;
estimate "2|ActvsPbl|Slope/mn" intercept 0 month 0 ttrrnd*month -2 1 1 / cl divisor=2;
```

- Shared-baseline mixed model with pMI for missing data: The shared-baseline mixed model with fixed effects for visits described above for the primary analysis will be applied to datasets generated by placebo multiple imputation (Ayele et al. 2014). Fifty imputed datasets will be generated for a given endpoint.
- PP sample: The primary efficacy model and the secondary random-slopes model and active vs. placebo estimand will be applied to the PP sample.
- loRMT sample: The primary efficacy model and the secondary random-slopes model and active vs. placebo estimand will be applied to the loRMT sample.

- AllQual sample: The primary efficacy model and the secondary random-slopes model and active vs. placebo estimand will be applied to the AllQual sample.

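### The exploratory splits on baseline SICI and baseline MEP amplitude rest on one pre-dose TMS session although two are collected; averaging the two would reduce avoidable misclassification at almost no cost.

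*SAP*

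**What the plan says.** SAP 3.8.6 gives one general rule: "Baseline values for efficacy endpoints will be determined from the last non-missing data collected prior to the first dose". SAP 3.8.4 lists the subgroups as "baseline SICI (median split), baseline MEP amplitude (median split), and baseline riluzole use (yes vs. no". They are analysed for the primary and key secondary outcomes in the mITT sample. That section does not define baseline again, so the 3.8.6 rule applies.

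Two TMS sessions precede treatment. Protocol 8.1 requires neurophysiological testing at Screening, and Protocol 8.2 requires it again at Baseline, no more than 21 days later. The schedule notes in SAP 2.8 say "Administer first dose of study drug AFTER all Baseline Visit procedures are completed", with only the ECG excepted, so the Baseline session is also pre-dose.

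The primary analysis treats the two sessions alike. SAP 3.8.1 specifies "fixed effects for visit (6 levels: Screening, Baseline, and Weeks 4, 6, 8, and 12" and sets every pre-treatment observation to month 0. SAP 3.2.1 defines the endpoint as change from pre-treatment rather than from a last value. The active-versus-placebo contrast in SAP 3.8.2 is written as "2 2 0 -2 -2 0 -1 -1 0 1 1 0 -1 -1 0 1 1 0". With the stated sort order, the first two coefficients belong to Screening and Baseline in the placebo arm, and they are equal; the same holds in each active arm.

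**The concern.** A subgroup defined by a measured quantity inherits that quantity's measurement error. Error in the moderator puts some participants in the wrong half, which mixes the halves and pulls any real difference in treatment effect toward zero. Protocol 13.2 treats session-to-session variation in TMS as real: it models within-person variance, defines a person-level intraclass correlation, and takes test-retest variation into account when sites are activated.

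Whether ezogabine acts differently by baseline SICI is a question the SAP chose in advance. With about 120 participants in three arms, a subgroup contrast has little information to spare. Part of the dilution could be removed with data already collected, by following the pre-treatment concept that the SAP uses for its primary endpoint.

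**Working it through.** **The plan's figures.** The documents give no figure for this point. The nearest is the sample size (SAP 3.4): 40 per arm for a 25-point difference, SD 30, two-sided alpha 0.027, 80% power and 25% loss. A two-sample t-test needs 29 evaluable per arm, and 29 / 0.75 = 38.7, so 39, in line with the stated 40. That calculation does not involve the subgroup baseline; N, power and alpha are unchanged by what follows.

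**Inputs.** Two pre-dose sessions (Protocol 8.1 and 8.2); a split at the median (SAP 3.8.4); about 120 randomized participants (SAP 2.4). Single-session reliability *r* is an assumption, shown at 0.5, 0.6 and 0.8. Errors are taken as normal, independent and equal in variance across sessions, with two valid sessions per participant.

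**Formulas.**
- Reliability of the mean of two sessions: *R* = 2*r* / (1 + *r*).
- The correlation between true and observed value is the square root of the reliability, so the share on the wrong side of the median is *m* = arccos(√reliability) / π.
- Share of a true between-half difference retained, if the treatment effect jumps at the true median: 1 − 2*m*.
- Share retained if the effect changes linearly with the moderator: √reliability.

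**Worked case, *r* = 0.6.** *R* = 1.2 / 1.6 = 0.75. One session: *m* = arccos(√0.6) / π = 0.218. Two sessions: *m* = arccos(√0.75) / π = 0.167. Step effect: 1 − 2(0.218) = 0.564, against 1 − 2(0.167) = 0.667 (unrounded *m* = 1/6). Linear effect: √0.6 = 0.775, against √0.75 = 0.866.

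| *r* | *R* | Misclassified, one vs two sessions | Of 120 | Retained, step | Retained, linear |
|---|---|---|---|---|---|
| 0.5 | 0.667 | 25.0% vs 19.6% | 30 vs 24 | 0.500 vs 0.608 | 0.707 vs 0.816 |
| 0.6 | 0.750 | 21.8% vs 16.7% | 26 vs 20 | 0.564 vs 0.667 | 0.775 vs 0.866 |
| 0.8 | 0.889 | 14.8% vs 10.8% | 18 vs 13 | 0.705 vs 0.784 | 0.894 vs 0.943 |

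A simulation of 1,000,000 draws agreed with the misclassification formula to within 0.001. At *r* = 0.6 the relative gain is about 18% under a step effect (0.667 / 0.564) and about 12% under a linear one (0.866 / 0.775).

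**The case against.** The best defence is that the last pre-dose value is a clear, prespecified and reproducible rule. It sits under the missing-data heading, where it also supplies a fallback when the Baseline session is absent. Session error is already limited: SAP 3.3.1 takes geometric means of replicates and applies central quality review, and Protocol 13.2 considers test-retest variation before activating a site. These points stand. They bear on how large the error is, but do not explain why the second session is left out of the splits.

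There is also a reason to prefer the later value. Inclusion criterion 10 (Protocol 5.2.1) requires sufficient MEP amplitude and/or CMAP amplitude at entry, so Screening MEP amplitude may be selected upward among those who qualified on it. SICI has MEP amplitude as its denominator, so some of this could carry over. How far is unknown, because the criterion can also be met on CMAP. The mean is therefore not a pure reduction in noise, and a last-value split should be kept as a check.

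Three stronger readings are tempting, and the documents support none of them.
- A reader might infer that the 3.8.6 rule weakens the efficacy analysis. It does not: the primary model keeps both pre-dose sessions as outcome rows, and SAP 3.8.3 applies the same models to RMT.
- A reader might infer bias between arms. The value precedes dosing and its error is the same in every arm, so the effect is dilution.
- A reader might want the mean for every variable measured twice. ALSFRS-R, SVC and dynamometry define no subgroup in 3.8.4 and follow a progressive disease, so a value up to 21 days older would move their baseline back in time.

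**Conclusion.** The point holds as a cheap improvement to two exploratory subgroup definitions. SAP 3.8.5 reports subgroup p-values as nominal, so no confirmatory claim depends on it. The only other use of these values touched here is the descriptive baseline table in SAP 3.6, where no consequence was identified.

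Over an assumed single-session reliability of 0.5 to 0.8, averaging would move about 4 to 5 percentage points of participants out of the wrong half. The gain in retained contrast depends on the shape of the effect: the step figures are the more favourable to the change, the linear ones the less. All figures assume two valid sessions for everyone; a participant with one gains nothing, so the realised benefit will be smaller to that extent. An attenuation factor for a continuous moderator would not describe this trial, because SAP 3.8.4 plans median splits.

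**What to change.** Add one sentence to SAP 3.8.4: for the median splits, baseline SICI and baseline MEP amplitude are each the mean, on the log scale, of the good-quality Screening and Baseline values, or the single good-quality value if only one exists. Repeat both splits with the last pre-dose value as a sensitivity analysis, which addresses possible upward selection of Screening MEP amplitude under inclusion criterion 10. Leave SAP 3.8.6 unchanged for all other variables.

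The reference to good quality also settles a small ambiguity: 3.8.6 speaks of non-missing data, while SAP 3.3.1 restricts primary TMS analysis to good-quality assessments. The cost is one sentence and one repeated run of each split. No new data are needed, and the sample size, alpha and primary model do not change.

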## 3.9 Safety Analysis

### 3.9.1 Treatment-emergent Adverse Events

The incidence of TEAEs will be summarized by the number of events of a given classification experienced by participants in each treatment group and by the number and proportion of participants experiencing such an event in each treatment group in the ST sample. TEAEs will be summarized in aggregate across all MedDRA terms and separately by MedDRA system organ class and preferred term.

Aggregate summaries of TEAE grade will include characteristics of: (a) seriousness, (b) severity, (c) relatedness to study drug, (d) relatedness to TMS, (e) relatedness to TTNCs, (f) action taken with study drug, (g) action taken with study procedure, and (h) outcome. For each level of a given TEAE characteristic, summaries will include the number of events of a given classification and by the number and proportion of participants for which that level of a characteristic was the worst they experienced (treating any unknown characteristic as not worst).

### 3.9.2 Suicidality

The proportion of participants who report any post-baseline suicidal ideation or any post-baseline suicidal behavior will be summarized by treatment group. Suicidal behaviors will include: actual attempts, non-suicidal self-injurious behavior, interrupted attempts, aborted attempts, preparatory acts or behaviors, and completed suicide. The most severe ideation, maximal frequency, maximal duration, minimal controllability, minimal deterrents, maximal reasons for ideation, maximal actual lethality or medical damage, and maximal potential lethality will be summarized as means, standard deviations, medians, and ranges by treatment group.

### 3.9.3 Safety Labs

The absolute level and the absolute change from baseline for each safety laboratory assay will be summarized as means, standard deviations, medians, and ranges at each visit by treatment group. The proportion of participants with safety lab levels below the lower limit of normal or above the upper limit of normal will be summarized by treatment group by visit and at any post-baseline visit.

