## 5.2.2 Exclusion Criteria

Study subjects meeting any of the following criteria during screening evaluations will be excluded from entry into the study:

1. Medical condition, laboratory finding, or physical exam finding that precludes participation.
2. Serum AST or ALT value >2.0 times the upper normal limit
3. Clinically significant conduction abnormalities on electrocardiogram or a known history of cardiac arrhythmia, myocardial infarction within the past 24 months, or congestive heart failure.
4. Estimated glomerular filtration rate < 50 mL/min at Screening Visit.
5. Concomitant digoxin treatment.
6. Known allergic reactions to components of the study product(s).
7. Exposure to any other agent currently under investigation for the treatment of patients with ALS (off-label use or investigational) within 30 days of the Screening Visit including ezogabine, exposure to cell replacement therapy within six months of the Screening Visit or any prior intraparenchymal cell replacement injection within the spinal cord or brain at anytime in the past.
8. Presence of tracheostomy at the Screening Visit.
9. History of clinically significant urinary retention, or current use of medications to treat urinary retention.
10. History of drug and or alcohol abuse within 12 months of the Screening Visit.
11. The presence of unstable psychiatric disease, cognitive impairment, or dementia that would impair ability of the subject to provide informed consent, according to SI judgment.
12. Clinically significant history of unstable or severe cardiac, oncologic, hepatic, or renal disease, or other uncontrolled medical condition.
13. Presence of feeding tube.
14. Current use of antipsychotic, antiepileptic (except benzodiazepines, gabapentin, pregabalin) or class 1 (e.g. flecainide) or class 3 (e.g. amiodarone) antiarrhythmic medications. Quinidine or a quinidine-containing drug is allowed if the quinidine dose is not greater than 20 mg/day (for a full list of medications, please reference the study MOP).
15. Pregnant women or women currently breastfeeding.
16. Contraindication to TMS studies including ferromagnetic metal in the head or neck (potentially found in aneurysm clips, implanted medication pumps, implanted brain stimulators, pacemakers, cochlear implants), or history of epilepsy. Dental fillings are permitted.

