### **10.1.7 Columbia Suicide Severity Rating Scale (C-SSRS)**

The US FDA recommends the use of a suicidality assessment instrument that maps to the Columbia Classification Algorithm for Suicide Assessment (C-CASA) (Posner et al., 2007). The C-CASA was developed to assist the FDA in coding suicidality data accumulated during the conduct of clinical trials of antidepressant drugs. One such assessment instrument is the Columbia Suicide Severity Rating Scale (C-SSRS) (US FDA Draft Guidance, 2010). The C-SSRS involves a series of probing questions to inquire about possible suicidal thinking and behavior.

At the Baseline Visit, the C-SSRS Baseline version will be administered. This version is used to assess suicidality over the subject's lifetime and specifically for the previous 6 month time period. Suicidality will also be assessed at follow-up visits over the course of the study.

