### 16.3 Appendix III: Columbia-Suicide Severity Rating Scale (C-SSRS) Baseline Version

Information obtained from: <http://www.cssrs.columbia.edu/>

SUICIDAL IDEATION	
Ask questions 1 and 2. If both are negative, proceed to "Suicidal Behavior" section. If the answer to question 2 is "yes", ask questions 3, 4 and 5. If the answer to question 1 and/or 2 is "yes", complete "Intensity of Ideation" section below.	Lifetime: Time He/She Felt Most Suicidal
1. Wish to be Dead Subject endorses thoughts about a wish to be dead or not alive anymore, or wish to fall asleep and not wake up. Have you wished you were dead or wished you could go to sleep and not wake up? If yes, describe:	Yes No  
2. Non-Specific Active Suicidal Thoughts General, non-specific thoughts of wanting to end one's life/commit suicide (e.g., "I've thought about killing myself") without thoughts of ways to kill oneself/associated methods, intent, or plan. Have you actually had any thoughts of killing yourself? If yes, describe:	Yes No  
3. Active Suicidal Ideation with Any Methods (Not Plan) without Intent to Act Subject endorses thoughts of suicide and has thought of at least one method during the assessment period. This is different than a specific plan with time, place or method details worked out (e.g., thought of method to kill self but not a specific plan). Includes person who would say, "I thought about taking an overdose but I never made a specific plan as to when, where or how I would actually do it...and I would never go through with it." Have you been thinking about how you might do this? If yes, describe:	Yes No  
4. Active Suicidal Ideation with Some Intent to Act, without Specific Plan Active suicidal thoughts of killing oneself and subject reports having some intent to act on such thoughts , as opposed to "I have the thoughts but I definitely will not do anything about them." Have you had these thoughts and had some intention of acting on them? If yes, describe:	Yes No  

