### 3.2.2 Safety Endpoints

The following safety endpoints will be evaluated:

- Proportion of participants experiencing and number of unique events of each type of TEAE and serious TEAE classified by MedDRA system organ class and preferred term,
- Proportion of participants experiencing and number of unique events of TEAEs classified by seriousness, severity, relatedness to study drug, relatedness to TMS and TTNCS procedures, action taken with study drug, action taken with TMS/TTNCS, and outcome, summarized across all MedDRA terms,
- Instances of treatment-emergent laboratory abnormalities classified by assay, whether the abnormality is below or above the normal range, and extend of deviation from normal,
- Mean change from baseline in weight
- Proportion of participants experiencing treatment-emergent clinically significant ECG abnormalities
- Proportion of participants experiencing treatment-emergent ophthalmologic complication,
- Mean change in AUA Symptom Score and proportion of participants with mild, moderate, or severe symptoms by visit,
- Proportion of participants reporting any treatment-emergent suicidal ideation
- Maximum post-baseline suicidal ideation planning, frequency, duration, controllability, deterrents, and reasons
- Proportion of participants reporting any post-baseline suicidal behavior, actual attempts, non-suicidal self-injurious behavior, interrupted attempts, aborted attempts, preparatory acts or behaviors, or completed suicide
- Maximum post-baseline suicidal behavior lethality and potential lethality

Reported proportions will use as their denominator all participants in the Safety and Tolerability sample (see Section 3.5 below).

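### SAP 3.2.2 defines laboratory abnormalities and suicidal ideation as treatment-emergent, but SAP 3.9.2 and 3.9.3 count any post-baseline occurrence, so the planned tables do not deliver the endpoints as defined

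*SAP*

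**What the plan says.** **Endpoints.** SAP 3.2.2 lists "Instances of treatment-emergent laboratory abnormalities classified by assay, whether the abnormality is below or above the normal range", and adds the extent of the deviation as a third classifier. It also lists "Proportion of participants reporting any treatment-emergent suicidal ideation". For suicidal behavior the same list uses the term post-baseline. Proportions are to be taken over all participants in the Safety and Tolerability (ST) sample.

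**Analyses.** SAP 3.9.3 reports level and change from baseline for each assay as means, standard deviations, medians and ranges. It then reports "The proportion of participants with safety lab levels below the lower limit of normal or above the upper limit of normal", by visit and at any post-baseline visit. SAP 3.9.2 reports "The proportion of participants who report any post-baseline suicidal ideation", together with behavior, and summarizes the most severe ideation.

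**Baseline.** The SAP does not define treatment-emergent for either endpoint. Its one rule for choosing a baseline value (3.8.6) covers efficacy endpoints only. In the schedule of assessments, safety labs are drawn at Screening and at Weeks 4, 6, 8 and 12, not at the Baseline Visit. Among the exclusions in protocol 5.2.2 is "Serum AST or ALT value >2.0 times the upper normal limit". Protocol 10.1.7 says the baseline C-SSRS covers lifetime and "specifically for the previous 6 month time period", while the form in Appendix III has one ideation column, headed "Lifetime: Time He/She Felt Most Suicidal".

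**The concern.** The endpoint list and the analysis sections ask different questions. The first asks who became abnormal, or began to report ideation, after starting study drug. The second asks who was abnormal, or reported ideation, at any time after baseline. Treatment-emergent and post-baseline do not look like loose synonyms here, because 3.2.2 uses one for ideation and the other for behavior.

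The eligibility rule lets participants enter with AST or ALT between 1 and 2 times the upper limit of normal (ULN). Anyone who does so and stays there is counted as abnormal in the post-baseline table. Because that table uses a single in-or-out flag, it also does not grade deviations, although 3.2.2 asks for that. Protocol 2.3.1.1 names liver-test elevation as a risk of the drug and increased suicide risk as a risk of anti-epileptic drugs as a class. These are two of the safety questions on which new occurrence needs to be told apart from pre-existing status.

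**Working it through.** **1. Text comparison.**

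| Item | SAP 3.2.2 | SAP 3.9.2 / 3.9.3 | Match |
|---|---|---|---|
| Labs, timing | treatment-emergent | any post-baseline visit | no |
| Labs, grading | extent of deviation | outside the range or not | no |
| Ideation | treatment-emergent | any post-baseline | no |
| Suicidal behavior | post-baseline | post-baseline | yes |

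No other section supplies the missing emergence rule or the extent bands. The documents state no figure for this point, so there is nothing to reproduce.

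**2. Illustration: inputs.** From the documents: 40 per arm (SAP 3.4) and the all-ST denominator (SAP 3.2.2). Assumed, because the documents do not give them:

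- b, the share abnormal at entry: 20%, range 10% to 30%.
- Persistence: everyone abnormal at entry stays abnormal.
- r, the emergent rate among those normal at entry: 2% on placebo, 20% on active.
- Worsening from an already abnormal baseline is ignored.

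**3. Formulas.** Over all ST participants, the treatment-emergent proportion is (1 − b) × r. The any-post-baseline proportion is b + (1 − b) × r.

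**4. Central case, b = 20%.** Treatment-emergent: 0.8 × 2% = 1.6% against 0.8 × 20% = 16.0%. Any post-baseline: 20% + 1.6% = 21.6% against 20% + 16.0% = 36.0%.

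**5. Range.** Power is for an exact two-sided Fisher test at 0.05 with 40 per arm. It serves only as a yardstick.

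| b | Emergent, placebo vs active | RR | Power | Any post-baseline, placebo vs active | RR | Power | Risk difference, both definitions |
|---|---|---|---|---|---|---|---|
| 10% | 1.8% vs 18.0% | 10 | 56% | 11.8% vs 28.0% | 2.4 | 36% | 16.2 points |
| 20% | 1.6% vs 16.0% | 10 | 46% | 21.6% vs 36.0% | 1.7 | 22% | 14.4 points |
| 30% | 1.4% vs 14.0% | 10 | 35% | 31.4% vs 44.0% | 1.4 | 15% | 12.6 points |

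The risk difference is the same in each row because b is added to both arms.

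**6. Chance imbalance.** The standard deviation of the between-arm difference in entry abnormality is √(2b(1 − b)/40). This is 6.7, 8.9 and 10.2 percentage points at b = 10%, 20% and 30%. Under full persistence, all of it passes into the any-post-baseline comparison.

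**7. Lower emergent rates.** With r = 1% against 10% and b = 20%, the treatment-emergent proportions are 0.8% against 8.0% and the any-post-baseline proportions 20.8% against 28.0%. Power is 7% and 8%. The choice of definition then makes no practical difference to a test, although the risk ratio still falls from 10 to 1.3.

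**The case against.** The strongest reply is that these are descriptive tables and that the named risks are covered elsewhere. Much of this stands.

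- SAP 3.9.2 and 3.9.3 plan no test and no risk ratio for these proportions, so the power figures are illustrative only.
- The change-from-baseline summaries include ranges, so an extreme liver value would be visible. By-visit proportions may also show Screening prevalence by arm.
- Clinically significant laboratory findings are adverse events under protocol 11.1.1 and so reach the TEAE tables (SAP 3.9.1). Possible drug-induced liver injury is an event of special interest, reportable within 24 hours.
- Follow-up visits use the Since Last Visit C-SSRS, so lifetime history alone is never counted. Only ideation that continues or recurs can be misread as new. SAP 3.9.2 also keeps severity, through the most severe ideation.
- The assumed 20% active rate is far above the 1-2% for liver-test elevation in protocol 2.3.1.1. Eligibility permits abnormal entry values but does not show that they are frequent.

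What this does not answer is that no planned table counts participants who became abnormal, or whose ideation was new. Group ranges and adverse event reports do not replace the endpoint that the SAP itself lists.

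Two stronger readings are tempting, and the documents support neither. A reader might infer that the drug effect shrinks on every scale; with the all-ST denominator the expected absolute risk difference does not change. A reader might also compare 22% power with the 64% that 2% against 20% gives when nobody is abnormal at entry. That mixes two populations. With 20% abnormal at entry, the like-for-like starting point is 46%.

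**Conclusion.** The inconsistency is real. As written, the analyses do not produce the laboratory and ideation endpoints that SAP 3.2.2 defines, and persistent pre-dose abnormality is counted as post-baseline abnormality. The cost falls on the risk ratio, on the precision of the comparison and, for labs, on the grading of abnormalities.

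How large the cost is cannot be read from the documents. The central illustration (risk ratio 10 to 1.7, power 46% to 22%) rests on assumed entry prevalence, full persistence and a high emergent rate. At 1% against 10% it has almost no bearing on power. Change-from-baseline ranges and the TEAE tables mitigate in part. The point should be corrected before the tables are produced. Confidence is high on the mismatch and low on its size.

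A reader might also conclude from the lifetime-only form that new ideation cannot be identified at all. That goes too far: for a participant with no lifetime ideation at baseline, any later report is new. The difficulty is confined to those with earlier ideation, for whom the printed form gives no recent reference.

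**What to change.** **SAP 3.9.3.** Take the last pre-dose sample as the safety baseline; by the schedule this is normally the Screening sample. Count a value as treatment-emergent only if it is newly outside the range or in a worse band than at baseline. Add shift tables from baseline to worst post-dose value, by multiples of the limit.

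**SAP 3.9.2.** Count ideation as treatment-emergent only if it is new, or of a higher type (1 to 5) than the pre-dose level.

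**Both sections.** Keep the any-post-baseline proportions as supplementary summaries.

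**Separately.** Reconcile the 6-month recall in protocol 10.1.7 with the lifetime-only form in Appendix III, and state which pre-dose reference period the collected data support. Changing the form is probably no longer useful: SAP version 1.0 is dated 27 Sep 2018, and SAP 3.7 describes the dropped interim analysis in the past tense, with final randomization already scheduled.

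**Cost.** SAP wording and two table shells. The laboratory data and the baseline C-SSRS are already in the schedule, so no new data collection is needed.
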